10.5.2. Subject Disposition

A detailed description of subject accountability including count of subjects included, exposed, completed (i.e., subjects who complete the study treatment) and discontinued along with the main reason for discontinuation will be generated for each cohort and for all subjects. All withdrawals from the study, taking place on or after study drug injection, will be fully documented in the body of the Clinical Study Report.

Note that the actual study duration is for a period of maximum 2 months, with efficacy analyses being conducted at 28 days and 56 days.

10.5.3. Demographic and Baseline Characteristics

Baseline will be defined as the last available and evaluable parameter value before and closest to the injection. If a rechecked value is used for baseline, it should be collected under the same conditions as for the planned baseline.

Baseline safety data will be presented along with subsequent safety values assessed during or after dosing.

10.5.4. Primary Safety Endpoint

The incidence of intolerable side effects will be presented overall and by cohort along with two sided 95% exact binomial Confidence Interval (CI).

10.5.5. Efficacy Analysis

Percent changes from baseline in local fat reduction (circumference of the leg above the knee, nodules size and/or numbers in the injected area) and tissue changes (fat thickness), will be presented in tabular form by visit.

Changes in nodular quality, local pain, quality of life and function will be presented in tabular form by visit and cohort.

10.5.6. Safety and Tolerability

Safety analyses will be descriptive in nature.

All reported AEs will be coded to a standard set of terms using MedDRA coding dictionary (V19.1 or higher) treatment.

AEs and tolerability data will be presented descriptively by treatment and cohort. AEs will be tabulated by body system, preferred term, seriousness, severity and relation to study drug by cohort. Where applicable, changes in values over time (e.g., lab values, vital signs, ECGs) will be presented; this will include clinical laboratory evaluations (including CBC, blood chemistry and urinalysis), coagulation (INR, PTT and PT), cytokines, vital signs, and ECGs. Shift tables of normal / abnormal versus baseline may be presented as well.

Draize scores will be presented in tabular format by visit, treatment, and cohort.

10.6. HANDLING OF MISSING DATA

No imputation of missing data will be performed.

10.7. INTERIM ANALYSIS

No interim analysis is planned.

11. DATA COLLECTION, STUDY MONITORING, AND DATA DISCLOSURE

11.1. DATA COLLECTION AND REPORTING

Each study subject will be assigned an individual CRF that will contain all of the relevant study information. The investigator shall ensure that all data is completely and accurately recorded on the CRFs throughout trial duration.

Data reported on the CRF that are derived from source documents should be consistent with the source documents or the discrepancies should be explained.

All fields and blanks in the CRFs will be completed. The following abbreviations are to be used when values or answers are not available: NA = Not applicable, ND = Not done, UNK = Unknown, CONT = Continued.

White-out or erasure on the CRF is not permitted under any circumstances. Any change or correction to a CRF should be dated, initialed, and explained (if necessary) and should not obscure the original entry (i.e., an audit trail should be maintained). If an entry on a CRF form is changed, the correction will be made as follows: A single line will be drawn through the incorrect entry, the date and initials of the reporting individual will be added beside the entered change and/or correction, and an explanation will be added when applicable.

When a subject withdraws from the study, regardless of cause, all final study evaluations should be attempted.

If a subject is lost to follow-up, (i.e., fails to return for scheduled visits) every reasonable effort must be made to contact the subject in order to determine why the subject failed to return. All actions taken in this regard will be documented and dated in the CRF.

Once completed, a copy of each completed CRF will be signed and dated by the investigator or a designated representative and submitted to the Sponsor.

11.2. RECORD KEEPING

The investigator will maintain all records for this study including medical records, laboratory reports, ICFs, safety reports, subjects' CRF, and any other pertinent data. All records are to be retained by the investigator for a period of fifteen years after completion of the study.

11.3. SOURCE DATA AND SOURCE DOCUMENTS

ICH-GCP defines source data as all information in original records and certified copies of original records of clinical findings, observations, or other activities in a clinical trial necessary for the reconstruction and evaluation of the trial. Source data are contained in source documents (original records or certified copies).

Source documents are defined as original documents, data, and records (e.g., hospital records, clinical and office charts, laboratory notes, subject files, and records kept at departments involved in the clinical trial, etc.).

The following data is to be recorded directly on the RZL-012 trial forms or CRF, which will be considered to be the source data:

- Subjects' questioning, e.g., pain, itching, topical antihistamine application.
- Assessment of AEs relation to investigational product, i.e., causality assessment, and expectedness reported by investigator.

The investigator should maintain the trial's essential documents as required by ICH-GCP guidelines and the applicable regulatory requirements, and take measures to prevent accidental or premature destruction of these documents.

Upon request of the monitor, auditor, IRB/EC, or regulatory authority, the investigator will ensure direct access to all requested trial-related records.

11.4. STUDY MONITORING

Monitoring procedures are required to assure compliance to ICH-GCP guidelines, the study protocol and local regulations.

The investigator shall allow the Sponsor or its official designee to monitor and audit periodically, at mutually convenient times, all CRF and corresponding subject records. The monitoring schedule will be based on Sponsor's monitoring plan and will be done by competent monitors per GCP by either Sponsor personnel or sponsor's designee such as a Clinical Research Organization (CRO).

11.5. CONFIDENTIALITY, DATA DISCLOSURE, AND PUBLICATION

In order to protect subject confidentiality, a consecutive identification number will be attributed to each subject enrolled to the trial. In order to avoid identification errors, this number and subject's initials (first letter of first name and the first letters of surname) will identify the subject and must be included on all CRFs. The investigator will complete subject identification on a confidential site log, which will be used for subjects' traceability and follow-up.

Individual subject medical information obtained as a result of this study is to be considered confidential and disclosure to third parties other than the regulatory authorities, or other persons or organizations designated by the Sponsor, is prohibited. Any medical information may be provided to the subject's personal physician or to appropriate medical personnel responsible for the subject's care. Additionally, data generated from this study is to be provided, upon request, to the Sponsor's monitors, as well as to the local IRB/EC. Subject confidentiality is to be further assured by utilizing subject identification code numbers to identify subject data.

All information supplied by Raziel Therapeutics Ltd. in connection with this study and not previously published, is considered confidential information. This information includes, but is not limited to, the IB, clinical protocol, CRF, and other scientific data. Any data collected during the study are also considered confidential. This confidential information shall remain the sole property of Raziel Therapeutics Ltd, shall not be disclosed to others without the written consent of the Sponsor, and shall not be used except in the performance of this study. The information developed during the conduct of this clinical study is also considered confidential, and will be used by the Sponsor in connection with the development of the product. The information may be disclosed as deemed necessary by the Sponsor. To allow the use of the information derived from

this clinical study, the investigator is obliged to provide Raziel Therapeutics Ltd. with complete test results and all data developed in this study.

The Sponsor has full ownership of the original CRFs completed as part of the study.

By signing the clinical study protocol, the investigator agrees that the results of the study may be used for the purposes of national and international registration, publication, and information for medical and pharmaceutical professionals. The authorities will be notified of the investigator's name, address, qualifications, and extent of involvement.

The information obtained during this study may be made available to other investigators who are conducting similar studies.

It is agreed that, consistent with scientific standards, publication of the results of the study shall be made only as part of a publication of the results obtained by all sites performing the protocol.

Raziel Therapeutics Ltd. will disclose the results of the trial on the basis of the final analysis and following the revision of a draft manuscript by the investigators, unless posting would compromise publication in a peer-reviewed medical journal or contravene national laws or regulations. Study results may also be disclosed through presentations and abstract submissions at professional scientific meetings.

12. HUMAN SUBJECTS

12.1. DECLARATION OF HELSINKI

Both the PI and the Sponsor will ensure that the study is conducted in agreement with the Declaration of Helsinki, ICH-GCP, and the local laws and regulation.

12.2. INFORMED CONSENT

As described in Section 6.1.1.

12.2.1. LIABILITY AND INSURANCE CONDITIONS

Raziel Therapeutics Ltd. holds a clinical trial liability insurance policy.

A copy of the policy summary will be filled in the investigator's site file.

Appendix I: Trial Schedule of Events

Study Procedure	Screening Day	Baseline (Treatment)	Visit Schedule (Days 1 to 28)				
	Day ^a -(-14) through Day (-2)	Day ^a 0	Day 1	Day 3	Day 7	Day 14	Day 21
Signed informed consent	X						
Medical history	X						
Concomitant Medication	X						
Complete physical exam	X						
Pain measurement	X					X	
For lipedema subjects - QOL measurement	X					X	
Serology assays (HbSAg, HCV, HIV)	X						
Urine Drug Screen	X						
Height and weight	X						
For Dercum's disease subjects – ultrasound assessing nodules size (diameter) and quality	X						
For lipedema subjects – assessing fat thickness and nodular quality by ultrasound.	X						
For lipedema subjects – measurement of leg circumference above the knee	X	Pre ^c X					
For lipedema subjects – ultrasound assessing nodules to be injected		Pre ^c X					
For Dercum's disease subjects – ultrasound re-assessing nodules size		Pre ^c X					
Photography of site of injection	X		X		X	X	X
Serum Chemistry, Hematology ^b	X	Pre ^c X	X	X	X	X	
Urinalysis	X					X	
Draize score at the injected site ^d	X	Pre ^c X post ^c	X		X	X	X
Vital signs ^e	X	Pre ^c X post ^c	X		X	X	X
Injection of RZL-012		X					
ECG ^f	X	X post ^c	X			X	
Pulse rate ^g		X post ^c	X				
Subjects diary recording of analgesics use	X	X	X	X	X	X	X
AE assessment			X-----				

a. Study day is based on Day 0 defined as the day of RZL-012 injection.

- b. CBC, coagulation, serum chemistry analysis, renal and liver function, urinalysis, CPK, amylase measurement: before injection, 14d and 28d following injection
- c. Pre/post – refers to before/after injection respectively
- d. Draize score evaluation: before injection, 2h, 24h and 7d, 14d, 21d and 28d following injection
- e. Vital signs measurement: before injection, 2h, 24h and 7d, 14d, 21d and 28d following injection
- f. ECG is to be performed in triplicate for all measurements in given time point: 4h, 8h, 24h following injection
- g. Pulse rate measurements at given time points: 1h, 2h, 4h, 8h, 24h following injection in the opposite hand of blood sampling

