	
1. Hematology: Complete blood count (CBC) including White blood cell [WBC] differential values, Fibrinogen, and coagulation (International normalized ratio [INR], Partial thromboplastin time [PTT] and Prothrombin time [PT]).2. Serum chemistry analysis: sodium, calcium, potassium, phosphorus, glucose, liver enzymes (Aspartate aminotransferase [AST], Alanine aminotransferase [ALT], Lactate dehydrogenase [LDH], Creatine-kinase MM [CK-MM], Gamma-glutamyltransferase [GTPP], Alkaline phosphatase [ALP]), Bilirubin, Creatinine, Blood urea nitrogen [BUN], Total protein, Albumin, Amylase, Creatine phosphokinase [CPK], C-reactive protein [CRP]).3. Urinalysis: Nitrite, Sodium, Potassium, Calcium, Phosphate, Protein, Red blood cells (RBC), WBC, Blood, Glucose, Ketone bodies, Bilirubin, Urobilirubin, Urine specific gravity, Osmolality, and pH. 
- In addition, photography and evaluation of skin irritancy by Draize score of the injection site area.- For Dercum's disease subjects – ultrasound assessing nodules size (diameter) and quality. Determining which nodules are to be injected with a total of 40mg RZL-012.- For lipedema subjects – measurement of leg circumference above the knee and assessing fat thickness and nodular quality by ultrasound.- For lipedema subjects - QOL and function questionnaires. 
Baseline visit (Day 0):
 
- Pre-treatment: eligibility confirmation, vital signs, Draize score, leg circumference, clinical evaluation of local pain and tenderness to pressure and nodules size and/or numbers, blood sample for serum chemistry, and hematology baseline level will be taken.- Treatment - All injections will be administered 45 ° to the skin surface using a 1 mL Luer-lock syringe and a 30 G x 1/2" needle (the hole of the needle pointing into the fat layer).- Post treatment: ECG (4h and 8h ± 30min post injection), pulse rate (1h, 2h, 4h, 8h, 24h post injection in the opposite hand of blood sampling), vital signs (2h ± 30 min post injection), Draize score (2h post injection ± 30 min), adverse events (AEs) will be recorded. 
Schedule visits (Day 1-28):
 
- Day 1 following treatment will include: ECG, vital signs including pulse rate, Draize score, and photographs of the treated area, clinical evaluation of local pain and tenderness to pressure. Subjects will start applying an anti-histamine gel.- For safety reasons 24hr ± 2hr following injection, Blood samples for serum chemistry and hematology will be taken- Day 3 following treatment will include Serum chemistry and hematology.- Visits will take place every 7 days ± 1d from treatment till Day 28. During visits, all tests (physical exam, vital signs, ECG, clinical laboratory tests, urinalysis, Draize score, leg circumference above the knee, weight measurement, QOL and function questionnaires in lipedema subjects, clinical evaluation of local pain and tenderness to pressure and reduction in nodules size and/or numbers, photographs and ultrasound will be performed according to schedule (Table 2).- Subjects will be questioned for AEs every visit.- Subjects will record their daily use of analgesics. Diaries will be checked and data will be captured in the CRFs. 
Follow-up visit (Day 56):
 
- Subjects will be followed on Day 56 following injection.- A week before Day 56 visit, subjects will record their daily use of analgesics. Diaries will be checked and data will be captured in the CRFs.- Evaluation of the injected area will be performed by Draize score, photographs, QOL and function questionnaires in lipedema subjects, clinical evaluation of local pain and tenderness to pressure and reduction in nodules size and/or numbers.

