RZL-012 is a novel synthetic molecule enabling the conversion of white adipose tissue (WAT) into an activated thermogenic tissue at targeted anatomical sites. A single injection of RZL-012 into WAT is sufficient to trigger robust tissue remodeling. A chain of events begins with removal of WAT adipocytes by macrophages (liponecrosis), followed by an activation of remodeled cells that generate a futile cycle of ongoing energy conversion into heat. Temperature measurements of the site treated by RZL-012 reveal a persistent local increase in temperature (about 4 months in pigs). As long as these cells are active, the ensuing thermogenic tissue will consume free fatty acids (FFA) from the nearby surrounding adipose depots and further from glucose and FFA supplied via the blood stream.

The overall clinical plan for RZL-012 includes the completed exploratory (phase 0) study to evaluate the safety, thermogenesis, and pharmacodynamic response to RZL-012. An additional phase 2 study ([Study RZL-012-P2aUS-001.1](#)) in overweight and obese subjects to confirm the safety and pharmacodynamic effects of RZL-012 for the treatment of obesity will be initiated soon to explore the response to higher doses prior to the initiation of larger studies. The initial exploratory study ([Study RZL-012-P0US-001.3](#)) demonstrated that RZL-012 is well tolerated with no serious adverse events reported and that thermogenesis was evident at the injection site (abdomen) of RZL-012-treated obese subjects. Although not statistically significant (due to the initially tested low dose and a small-size study group, n=6), there was a decrease in subcutaneous fat mass (SFM) over time (compared to baseline) in the abdomen, as measured by Magnetic Resonance Imaging (MRI), in 5 out of 6 RZL-012 treated subjects, but none in vehicle treated ones.

Raziel Therapeutics believes that RZL-012 effects of adipose-tissue replacement thermogenic tissue and the ongoing lipolysis and consumption of FFA from nearby adipose tissue by the remodeled cells can be beneficial to patients with fat disorders such as lipedema and Dercum's disease. Local fat reduction and tissue remodeling at selected sites such as at the medial knee in lipedema patients and at lipomas in Dercum's disease patients may bring pain relief and improvement in QOL.

The current Phase 2a study is aimed to evaluate the safety and pharmacodynamics response to RZL-012 in lipedema and Dercum's disease patients.

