A slight elevation in body temperatures was noted in males treated with the test article from Days 14-16 until Days 77-79. In addition, several animals were observed with perioperative hyperthermia and/or hypothermia. To determine if the perioperative hyperthermia and/or hypothermia was caused by Porcine Stress Syndrome all remaining animals on study were tested and determined to be normal (negative).

Administration of the test article was associated with changes in subcutaneous fat temperatures, a mild increase in neutrophils, and macroscopic and microscopic observations.

A noticeable difference in subcutaneous fat temperatures was noted between treatment groups. Beginning as early as Day 4-5, an increase in temperature was noted at all test article treated sites

in both males and females. The increase in temperature was noted through Days 58-63. At study termination, subcutaneous fat temperatures at treated sites were comparable to vehicle control.

Subcutaneous administration of RZL-012 (50 mg/mL) to farm pigs resulted in mild increases in neutrophils in both sexes at the 24-hour post-dose collection, which were most typical of an inflammatory response. Increases in neutrophils had resolved by the Day 14 collection.

Analysis of the plasma samples following subcutaneous administration of RZL-012 (Group 4) found that both female and male farm pigs were exposed to RZL-012. Mean systemic exposure (area under the concentration versus time curve between zero and the 24 hour time point [AUC_{0-24hr}]) and maximum observed concentration (C_{max}) values, were 3700 (hr*ng/mL) and 529 (ng/mL), respectively, for males and mean systemic exposure (AUC_{0-24hr}) and C_{max} values, were 2940 (hr*ng/mL) and 528 (ng/mL), respectively, for females.

Upon evaluation of the injection site photographs, no irritation was observed but transient redness was noted. Upon microscopic evaluation at 24 hours and 14 days, test article related findings in the injected subcutaneous tissue was noted. These findings were characterized by necrosis of the subcutaneous fat and muscle accompanied by acute inflammation at 24 hours post-dose. At 14 days, residual necrotic tissue in the injected areas was noted with evidence of on-going healing characterized by chronic inflammation and fibrosis. There was no evidence of systemic toxicity at 24 hours or 14 days

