6.1.7. Vital Signs Measurements

Subjects' vital signs will be measured at Screening Day (performed 14 through 2 days prior to baseline) in order to ensure compliance with study inclusion criteria.

Vital signs measurements will include systolic and diastolic sitting position blood pressure, pulse rate, respiratory rate, and body oral temperature.

Additional vital signs measurements to assess subject's safety will be performed at baseline visit (Day 0) prior to drug injection, 2h ± 30min following drug injection, the following day (Day 1) after drug injection (24h ± 2h) and on study visits every 7 days thereafter, i.e., Day 7, Day 14, etc.

Additional pulse rate measurements to assess subject's safety will be performed at baseline visit (Day 0) prior to drug injection and 1h, 2h, 4h, 8h, 24h following injection in the opposite hand of blood sampling.

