6.2.4. Baseline Visit

Baseline visit is defined in the study as Day 0. Baseline visit will be performed to complete screening evaluation, and to review all procedures necessary to confirm subject eligibility. Subjects will stay under supervision in the study center till 8h + 3h following drug injection.

Screening information may be considered for baseline data if acquired within the adequate timeframe as described in Table 2.

Table 2: Subject Information and Timeframes

Information	Timeframe	Follow-up Timeframe
Informed Consent Form	Signed prior to any study dedicated procedure	
Medical History and Concomitant Medications	At Screening Day visit	
Physical examination	At Screening Day visit and at Day 28	
Pain Measurement	At Screening Day visit and at Days 14, 28	At Day 56
QOL Measurement in lipedema subjects	At Screening Day visit and at Days 14, 28	At Day 56
Vital Signs	At Screening Day visit and at Days 0 (pre and following injection), 1, 7, 14, 21, 28	
Pulse rate	At Day 0 (following injection) and at Day 1	
ECG	At screening Day 1 visit, at Day 0 (following injection) and at Days 1, 14, 28	
Draize Score at the Injected Site	At Screening Day and at Days 0 (pre- and following injection), 1, 7, 14, 21, 28	At Day 56
Serology assays (HbSAg, HCV and HIV)	At Screening Day visit	
Drug screen	At Screening Day visit	
Serum chemistry and Hematology	At Screening Day and at Day 1, 3, 7, 14 and 28	
Urinalysis	At Screening Day visit and at Days 14 and 28	

Information	Timeframe	Follow-up Timeframe
Ultrasound for nodules quality and size. Fat thickness – for lipedema	At Screening Day visit and at Day 28	At Day 56
Ultrasound for nodules size and selection for injection	At Days 0 (pre- injection)	
Photography of the Injected Sites	At Screening Day visit and at Days 1, 7, 14, 21, 28	At Day 56
AE Assessment	At Days 1, 3, 7, 14, 21, 28	At Day 56

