- A slight elevation in body temperatures was noted in male pigs.
- Sinus tachycardia (in pigs), occurring at the 4 hour interval post dosing.
- In addition, other acceptable treatment to relieve drug-related AE's should be used at Investigator's discretion.

Study subjects must be informed of possible AEs that occurred in clinical studies (phase 0):

- At the injection site -local and transient: erythema, edema, pruritus, anesthesia, pain, mass (subcutaneous scar).
- Abdominal abscess
- Transient moderate to severe elevation of the liver enzymes: ALT and AST.

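### Body temperature is not scheduled after Day 28, so the trial could not describe whether a rise like the one in treated male pigs persists or resolves (low severity, cheap to improve)

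*Protocol*

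**What the plan says.** **The animal finding.** Protocol Section 1.2.2.1.2 (Pigs) states: "A slight elevation in body temperatures was noted in males treated with the test article from Days 14-16 until Days 77-79". Section 7.2 repeats it, without a duration, among the possible adverse events that subjects must be told about: "A slight elevation in body temperatures was noted in male pigs".

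**How temperature is measured.** Section 6.1.7 defines the set: "Vital signs measurements will include systolic and diastolic sitting position blood pressure, pulse rate, respiratory rate, and body oral temperature". No other scheduled procedure measures body temperature.

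**When it is measured.**
- Appendix I, footnote e, repeated in SAP 5.4.2: "Vital signs measurement: before injection, 2h, 24h and 7d, 14d, 21d and 28d following injection".
- Table 2 (Section 6.2.4), vital signs row: "At Screening Day visit and at Days 0 (pre and following injection), 1, 7, 14, 21, 28". The follow-up cell, where other rows carry Day 56, is empty.
- Section 6.1.7 gives no last day: "on study visits every 7 days thereafter, i.e., Day 7, Day 14, etc".
- The synopsis visit schedule closes the weekly series: "Visits will take place every 7 days ± 1d from treatment till Day 28".

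**What happens on Day 56.** The synopsis lists Draize score, photographs, questionnaires for lipedema subjects, pain and nodule evaluation, ultrasound, leg circumference for lipedema subjects, and adverse event questions. Vital signs are not listed.

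**Use of the data.** Section 10.2.3 names vital signs as a safety endpoint. The SAP plans tables of values, changes and relative changes (14.4.2-1, 14.4-2.2, 14.4-2.3).

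**The concern.** The sponsor's own animal data describe a temperature change that begins about two weeks after injection and lasts about nine weeks. The trial stops scheduled temperature readings about two weeks into that interval, yet brings the same subjects back on Day 56 without taking one.

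What is at stake is description. Safety is the primary objective, and vital-sign change is a planned safety output. If a subject's temperature is raised on Day 21 or Day 28, the schedule supplies no later reading to show whether it settled. Adverse event questioning would pick up a symptomatic fever, but is unlikely to pick up a slight rise that the subject does not feel.

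**Working it through.** The plan gives no figure to reproduce, so the check is day arithmetic on the documents' own dates.

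**Inputs**
- Onset of the pig rise, S: Day 14 to 16 (Section 1.2.2.1.2).
- End of the pig rise, E: Day 77 to 79 (same place).
- Last scheduled human reading, L: Day 28 (Table 2; Appendix I footnote e), with a window of ±1 day (synopsis).
- Last planned visit: Day 56 (synopsis).

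**Step 1. Share of the pig period after the last reading** = (E − L) / (E − S), with L = 28.

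| S | E | Length (days) | Days after Day 28 | Share |
|---|---|---|---|---|
| 14 | 77 | 63 | 49 | 77.8% |
| 14 | 79 | 65 | 51 | 78.5% |
| 16 | 77 | 61 | 49 | 80.3% |
| 16 | 79 | 63 | 51 | 81.0% |

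So 49-51 of 61-65 days, or 78%-81%, fall after the last scheduled reading.

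**Step 2. Sensitivity to the visit window.** The lowest share is with a Day 29 reading: (77 − 29)/(77 − 14) = 48/63 = 76%. The highest is with a Day 27 reading: (79 − 27)/(79 − 16) = 52/63 = 83%.

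**Step 3. Counting only time within follow-up.** From onset to Day 56, the 28 days after Day 28 are 28/(56 − 14) = 67% to 28/(56 − 16) = 70%.

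**Step 4. What the present schedule can still detect.** Days 21 and 28 lie inside every version of the pig period, and Day 14 lies at its onset. A sustained rise with that time course would be sampled two or three times.

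**Step 5. What a Day 56 reading leaves open.** E − 56 = 21 to 23 days, which is 21/63 = 33% to 23/63 = 37% of the period. Between Day 28 and Day 56 there would be one reading, at the end.

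**Step 6. Is the Day 28 stop real?** Footnote e alone is weak evidence. Footnote d, in the same form, ends the Draize score at 28 days, while Section 6.1.11 and Table 2 extend that score to Day 56. The Day 28 and Day 56 columns of the Appendix I grid, and the end of the vital signs row in SAP 5.4.2, could not be read in the text reviewed. Table 2 and the synopsis carry the point: Table 2 gives the Draize score a Day 56 entry and gives vital signs none, and the synopsis Day 56 list agrees. The open wording of Section 6.1.7 does not supply a Day 56 reading, because the weekly visits it refers to stop at Day 28.

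**The case against.** The case for leaving the schedule alone has real weight.

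- **Detection is not lost.** A reader might infer that the trial could wrongly report no temperature effect. The documents do not support that: a rise on the pig time course would already appear at Days 21 and 28, and perhaps Day 14. The safety analysis is descriptive, and no such conclusion is planned. This objection stands, and it limits the point to persistence.
- **The animal signal is modest.** The rise was slight and in males only. The study's own list of changes associated with the test article names fat temperature, neutrophils and tissue findings, not body temperature. Pigs received 5.32 to 7.14 mg/kg. An 80 mg total would match the lower figure only at a body weight of 80/5.32 = 15 kg, so human exposure per kg is lower. Men can enter only cohort 1. This stands as a reason for low severity.
- **Earlier human data are reassuring.** The phase 0 study reported no clinically significant vital-sign changes. Its top dose was 20 mg, against stated maxima of 40 mg and 80 mg here, so it helps but does not settle the matter.
- **The primary endpoint is untouched.** A slight, symptom-free rise would not count as an intolerable side effect. This stands.
- **Other routes remain open.** Section 6.1.15 and Table 2 continue adverse event assessment to Day 56, and unscheduled visits may include any study procedure. It is therefore wrong to call the later period unobserved; temperature is simply not measured on schedule. (Section 9.5.1 gives different end points for adverse event capture, 28 days or 6 months in the highest dose cohort, and must be reconciled with these.)
- **The stop is coherent.** Table 2 ends vital signs, ECG, laboratory tests and physical examination together at Day 28. That is a defensible design choice, which makes this an improvement to consider and not an error.

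**Conclusion.** The point holds as a low-severity, nearly free improvement. As scheduled, the trial can detect a temperature rise in the first four weeks but cannot describe whether it lasts or resolves. On the pig time course, 49-51 of 61-65 days (78%-81%; 76%-83% allowing for the Day 28 visit window) would follow the last scheduled reading.

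This rests on treating pig days as human days, which the documents do not establish, and on Table 2 and the synopsis correctly stating the intended Day 56 content.

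Two stronger readings should be resisted. A reader might link the gap to the background statement that treated sites "reveal a persistent local increase in temperature (about 4 months in pigs". That describes local heat at the injection site, which an oral reading does not measure. A reader might also say that a Day 56 reading would extend coverage of the pig period to about 65%: on midpoints of Day 15 and Day 78, (56 − 15)/(78 − 15) = 41/63. That treats one reading as continuous observation over 28 days. It would show only whether a change was still present on that day.

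**What to change.** 1. Add vital signs, including oral temperature, at Day 56 in the follow-up column of Table 2, in Appendix I and its footnote e, in the synopsis Day 56 list, and in SAP 5.4.2 with its footnote.
2. In Section 6.1.7, replace the open-ended wording with the explicit list of days, so that it matches Table 2.
3. Report Day 56 in SAP Tables 14.4.2-1, 14.4-2.2 and 14.4-2.3.

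**Cost.** A few minutes per subject, for at most 12 subjects, at a visit already planned; one more time point in existing tables; and a wording change to the protocol and SAP. No new visit, staff or equipment is needed.

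**What it does not buy.** The last 21-23 days of the pig period stay beyond planned follow-up. The report should describe the Day 56 value as a single check on persistence.
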